#### **7.5 Visit 5: Follow-up Visit**

The follow-up visit will be conducted within 7 days after the completion of the third condom assessment period (or earlier if the subject has reported a minimum of 4 IELT duration records) or within 7 days in the event of a subject's withdrawal from the clinical investigation. Clinical assessments consisting of a physical examination (if necessary in the opinion of the investigator), vital signs recording, concomitant medication, AEs/ ADEs review will be carried out.

Subjects are to return all unused condoms, used/unused lubricant(s) (if supplied) and the investigation stopwatch. The Investigator or delegate will examine diaries and questionnaires for completeness. All assessments conducted during follow-up visit are detailed in [Section 6](#) and summarised in [Table 7-1](#). All clinical assessments and test results will be entered into each subject's eCRF.

	Clinical Investigation Plan		
	Investigation No: 5078401	Protocol Version: V2.0 08-Jun-2023	Page 45 of 62

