### **Benzocaine**

The adverse reactions associated with benzocaine are also well known and include local irritation and sensitisation and more rarely hypersensitivity, cyanosis and methemoglobinemia.

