Subjects will attend the clinical site on 5 occasions: one screening visit, three assessment period visits and one follow-up visit. Screening includes a 4-week baseline period, which allows the subject and his partner to familiarise themselves with the use of the stopwatch method and completing IELT diaries. Eligible subjects will return to the clinical site, where they will be randomised and receive the first of the three condom types (according to the randomisation schedule). Subjects will be provided with 8 condoms per condom type. The process will be repeated until all three condom types have been used. The follow-up visit will occur within 7 days after the completion of the final condom assessment period. At least a 3-day washout period, where no test condom will be used, is required before subjects attend the clinical site for visit 3 and visit 4. The 3-day washout period is to mitigate the effects on any residual benzocaine across condom types.

The investigation design is outlined in the schematic below (Figure 3-1).

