## 6.11 Adverse Events

During visits to the clinical site non-leading questions will be used to collect any AEs/ ADEs. In addition, spontaneously reported AEs/ ADEs will be collected.

The observation period for an individual subject and his female partner will start after giving informed consent and will finish at the last visit (follow-up visit). All AEs/ ADEs that arise during the observation period will be recorded and an assessment of the AEs/ ADEs will be performed as per [Section 8.2](#) by a medically qualified Investigator. If a subject or his female partner has an AE/ ADE that is still ongoing at the last visit, an attempt will be made by the Investigator to follow this up as per [Section 8.4](#).

If an untoward medical occurrence happens after the subject has signed the consent form but before administration of the device, it should be reported as an AE, including those associated with investigation procedures.

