#### **7.4 Visit 3 and 4: Assessment Period 2 and 3**

Visits 3 and 4 will be conducted within 7 days after the completion of each condom assessment period weeks (or earlier if the subject has reported a minimum of 4 IELT duration records). A 3-day washout period, where no test condom will be used, is required before subjects attend the clinical site to return unused condoms and be supplied with their subsequent condom type. During the 3-day washout period, coital act is allowed with a 24 hour gap maintained between the last coital act or masturbation and the visit to the clinical site. Procedures and assessments will be the same as those performed in assessment period 1, except for randomisation, which is performed at Visit 2 only.

Subjects will be required to return all unused condoms of the first and second condom type (respectively). Following confirmation of continued eligibility, subjects will be provided with the alternative condom type from the kit to be used for the subsequent condom assessment period. Additional supply of lubricant will also be provided if required and the empty lubricant bottle/tube should be returned.

In the opinion of the Investigator, a subject who fails to remain eligible for the clinical investigation will be withdrawn.

The Investigator or delegate will examine diaries and questionnaires for completeness. Training and instruction on diary and questionnaire completion and safety reminder will be repeated as Visit 2.

All assessments conducted during assessment period 2 and 3 are detailed in [Section 6](#) and summarised in [Table 7-1](#). All clinical assessments and test results will be entered into the subject's eCRF.

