#### **8.4 Follow-up of Adverse Events**

All SAE / SADE / USADEs and all AE / ADEs that have not resolved by the end of the investigation will be followed up by the Investigator until resolution or until the Investigator believes there will be no further change, whichever is the earlier. This may involve the subject or the female partner making additional visits to the site.

In the case of loss to follow-up, at least two documented attempts to contact the subject must be made by the Investigator or designee before this is defined.

The end of the investigation is defined as the last visit of the last subject in the investigation.

All SAE/ SADE/ USADEs and all AE/ ADE that cause premature withdrawal of the subject and the female partner from the investigation and have not resolved by the end of the investigation will be followed up by the Investigator until resolution or until the Investigator believes there will be no further change.

This may involve the subject or the female partner making additional visits to the site. The minimum data required are the subject number, suspected investigational product, final outcome and date, which may be obtained by the Investigator in a documented telephone conversation with the subject/female partner or subject's/female partner's general practitioner (GP)/ Primary Care Physician (PCP).

Subjects/Female partners who experience the onset of an (S)AE after the last visit (end of the investigation) will not need to be recorded.

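### Adverse-event collection closes at Visit 5, which has no minimum interval after the last use of the third condom, so the final use or uses may go almost unobserved

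*Protocol*

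**What the plan says.** Before Visits 3 and 4, protocol 3.1 asks for at least 3 days without a test condom; the interval "is required before subjects attend the clinical site for visit 3 and visit 4". Visit 5 is not named. Section 7.4 repeats the rule for the visits at which the next condom type is handed over: "A 3-day washout period, where no test condom will be used, is required before subjects attend the clinical site to return unused condoms". Section 3.1 gives the reason: "The 3-day washout period is to mitigate the effects on any residual benzocaine across condom types".

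For Visit 5, section 7.5 sets only a latest time, 7 days after "completion of the third condom assessment period (or earlier if the subject has reported a minimum of 4 IELT duration records"). Table 7-1 and the synopsis set no earliest time either.

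On safety collection, section 6.11 says that the observation period for a subject and his partner "will start after giving informed consent and will finish at the last visit (follow-up visit"). Section 8.4 adds that those "who experience the onset of an (S)AE after the last visit (end of the investigation) will not need to be recorded". The same section defines the term in that parenthesis for the whole study: "The end of the investigation is defined as the last visit of the last subject in the investigation".

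The benefit-risk section says that known reactions to benzocaine "include local irritation and sensitisation and more rarely hypersensitivity".

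**The concern.** Safety and in-use tolerability are stated objectives. One safety endpoint is the proportion of subjects with at least one AE or ADE, summarised by condom and separately for men and women (protocol 9.5.2.1 and 9.6). How much an incidence captures depends on how long people are observed after exposure, and here that depends on the period. After condoms one and two there are at least 3 days, and the record stays open through the next period. After condom three the guaranteed time is nil, because the visit that closes the record may fall on the day of last use.

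A reaction that first appears after Visit 5 has no planned route into the data. This applies particularly to the partners. Under the notes to Table 7-1, their events come from spontaneous reports, questions put to the male subject at Visits 2 to 5, or the investigator's observation. Visit 5 is the last planned occasion for any of these.

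**Working it through.** **The plan's own figure.** The only stated number that depends on the timing of Visit 5 is the maximum participation of 19 weeks (protocol 4.1). Inputs: 4-week baseline, three condom periods of up to 4 weeks, and three 7-day visit windows (before Visits 3, 4 and 5).

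4 + 3 × 4 + 3 × 1 = 19 weeks.

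This reproduces the stated maximum, so the full 7-day window before Visit 5 is already counted in it.

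**Guaranteed AE observation after the last use of each condom.**

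| Condom in sequence | Guaranteed condom-free time before the next visit | AE collection after that visit |
|---|---|---|
| First | at least 3 days (3.1, 7.4) | continues through period 2 |
| Second | at least 3 days (3.1, 7.4) | continues through period 3 |
| Third | none stated (7.5, Table 7-1) | ends (6.11) |

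**Earliest permitted Visit 5.** Section 6.3 requires at least 24 hours between coital acts. Four records therefore take at least (4 − 1) × 24 = 72 hours from first use, and 7.5 then allows the visit. If four condoms are used at minimum spacing and the visit falls on the day of the fourth use, observation after each use is about:

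- use 1: 72 hours
- use 2: 48 hours
- use 3: 24 hours
- use 4: close to 0 hours

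The shortfall concerns the last use or uses, not the whole period.

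**How many subjects, and which condoms.** SAP 12.8 gives six sequences in blocks of six. Three condoms can be ordered in 3! = 6 ways, and each is last in 2 of them. With 150 randomised, 150 × 2/6 = 50 subjects per condom have that condom third; with 135 completers, 135 × 2/6 = 45. Over all condoms this is 150 of 150 × 3 = 450 subject-periods, or one third, spread evenly across the three types.

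**What cannot be computed.** The number of events missed needs a reaction rate, a distribution of time to onset and the actual timing of Visit 5. The documents give none of these. If every couple attends 3 or more days after last use, the third condom has the same minimum as the other two and the shortfall against that standard is zero. The more couples attend early, the larger it could be.

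**The case against.** The strongest reply is that the 3-day interval is a washout. Its purpose is carry-over, no condom follows Visit 5, and so a washout there would do nothing. That is correct. A reader might infer that 7.5 contradicts 3.1 and 7.4, but it does not. What remains is a side effect: the washout happens to guarantee some safety observation after two of the three condoms.

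Three further limits also stand.

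- One might read the design as leaving a third of all exposures unobserved. The spacing of acts rules that out, since earlier uses within the third period are followed by one or more days of collection. Events that begin before Visit 5 are recorded, and unresolved ones are followed under 8.4.
- The documents name reactions to benzocaine but give no time to onset. That some begin after Visit 5 is an assumption.
- One might say that a late reaction would certainly go unrecorded. Section 8.4 ties its release from recording to the end of the investigation, which it defines as the last subject's last visit, while 6.11 uses each subject's own follow-up visit. On the study-wide reading a spontaneous late report might still be recorded, although no contact is planned to elicit one.

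The text on the washout itself is also not fully settled. The Figure 3-1 footnote asks for 3 days before the next visit, and the figure is not available to show which visits it marks. SAP 9.3 asks whether the washout was kept before the visit without naming visits. Either could have been meant to cover Visit 5, but 3.1 names only Visits 3 and 4.

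**Conclusion.** The point holds as a gap in safety observation. A site that follows the plan exactly may close a couple's AE/ADE record on the day the third condom was last used, whereas at least 3 condom-free days with continuing collection follow the first two. This can affect the last use or uses of whichever condom came third, about 50 of 150 subjects for each condom.

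Absolute incidence could be understated, by an amount not derivable from the documents and possibly zero. The documents do not show that it is understated. They also do not support a claim of bias between condoms: balanced sequences spread the shorter window about equally over all three, provided that dropout and early attendance do not differ much by condom. The primary endpoint and the sample size are unaffected. It is worth correcting because the change is nearly free.

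**What to change.** Reconcile protocol 3.1, the Figure 3-1 footnote, 6.11, 7.4, 7.5, 8.4 and Table 7-1 so that AE observation after the last use of the third condom is not shorter than that already guaranteed after the first two, within the existing 7-day window. Bring the synopsis text on Visit 5 into line. Make the wording on late onsets in 8.4 agree with the subject-level last visit in 6.11, so that it is clear when recording stops for each couple.

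No new data item is needed. The IELT diary already records the date and time of each act, so the interval from last use to Visit 5 can be derived and summarised by condom.

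The cost is a few lines of text. No visit, procedure or staff time is added, and the 19-week maximum stays as it is. The drawback is that some couples would attend Visit 5 a few days later than they otherwise could.

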## 7.6 Unscheduled Visits

If unscheduled visits occur, the Investigator must record the reason for unscheduled visit in the subject's eCRF, including any AEs/ ADEs that the subject and his female partner have experienced since the subject's last visit, concomitant therapy changes, withdrawal (if deemed appropriate) and any clinical assessments deemed appropriate for the clinical care of the subject and/or his female partner.

Unscheduled visits should not alter the timing of the routine investigation schedule.

## 8 SAFETY REPORTING

The assessment and reporting of AEs in the investigation are in compliance with the Regulation (EU) 2017/745, the guidance of MDCG 2020-10/1 and guidelines on medical devices, MEDDEV 2.7/3 revision 3, May 2015.

### 8.1 Adverse Event Definitions

#### Adverse Event

An Adverse Event (AE) is any untoward medical occurrence, unintended disease or injury or any untoward clinical signs (including an abnormal laboratory finding) in subjects, users or other persons, in the context of a clinical investigation, whether or not related to the investigational medical device.

This definition includes events that are anticipated as well as unanticipated events.

This definition includes events occurring in the context of a clinical investigation related to the investigational device, the comparator or the procedures involved.

#### Adverse Device Effect

An Adverse Device Effect (ADE) is an AE related to the use of an investigational device.

This includes any AE resulting from insufficient or inadequate instructions for use, deployment, implantation, installation, operation, or any malfunction of the investigational medical device. This includes any event that is a result of a use error or intentional misuse.

#### Device Deficiency

Any inadequacy in the identity, quality, durability, reliability, safety or performance of an investigational device, including malfunction, use errors or inadequacy in information supplied by the manufacturer.

#### Serious Adverse Event

A Serious Adverse Event (SAE) is an AE that led to any of the following:

- a. Death,
- b. Serious deterioration in health of the subject, that resulted in any of the following:
  - a life-threatening illness or injury,
  - a permanent impairment of a body structure or a body function,

	Clinical Investigation Plan		
	Investigation No: 5078401	Protocol Version: V2.0 08-Jun-2023	Page 46 of 62

- hospitalisation or prolongation of patient hospitalisation,
- medical or surgical intervention to prevent life threatening illness or injury of permanent impairment to a body structure or a body function,
- chronic disease,

c. foetal distress, foetal death or a congenital physical or mental impairment or birth defect.

A planned hospitalisation for pre-existing condition, or a procedure required by the CIP, without a serious deterioration in health, is not considered to be an SAE.

This includes device deficiencies that might have led to a SAE if

- a. suitable action had not been taken or
- b. intervention had not been made or
- c. if circumstances had been less fortunate.

#### Serious Adverse Device Effect

A Serious Adverse Device Effect (SADE) is an ADE that has resulted in any of the consequences characteristic of a SAE.

#### Unanticipated Serious Adverse Device Effect

An Unanticipated Serious Adverse Device Effect (USADE) is an effect which by its nature, incidence, severity or outcome has not been identified in the current risk assessment.

#### Anticipated Serious Adverse Device Effect

Anticipated SADE (ASADE): an effect which by its nature, incidence, severity or outcome has been previously identified in the current risk assessment.

## **8.2 Assessment of Adverse Events**

All AEs that arise after the subject and his female partner have given informed consent will be recorded in the subject's source documents and CRF. AEs can be reported spontaneously by the subject/his female partner or in response to non-leading questioning, observation by the Investigator or be a significant laboratory abnormality.

All AEs, ADEs, SAEs, SADEs and USADEs are collected, fully investigated and documented.

SAE / SADE / USADEs should be followed until resolution or stabilisation. Subjects and their female partners with ongoing SAE / SADE / USADEs at investigation termination will be further followed up until recovery or until stabilisation of the disease after termination.

For each AE a causality assessment of the event to the investigational device, the comparator or the investigation procedure must be performed. The relationship to the investigational device, the comparator or the investigation procedure must be determined by the Investigator (if medically qualified) or by a medically qualified Co-Investigator.

	Clinical Investigation Plan		
	Investigation No: 5078401	Protocol Version: V2.0 08-Jun-2023	Page 47 of 62

Relationship	Description
Not related	
Relationship to the investigational device, comparator or procedures can be excluded when:
 
 
the event has no temporal relationship with the use of the investigational device or the procedures related to application of the investigational device.
 
the serious adverse event does not follow a known response pattern to the investigational device (if the response pattern is previously known) and is biologically implausible.
 
the discontinuation of investigational device application or the reduction of the level of activation / exposure - when clinically feasible - and reintroduction of its use (or increase of the level of activation / exposure), do not impact on the serious adverse event.
 
the event involves a body-site or an organ that cannot be affected by the device or procedure.
 
the serious adverse event can be attributed to another cause (e.g. an underlying or concurrent illness / clinical condition, an effect of another device, drug, treatment or other risk factors).
 
the event does not depend on a false result given by the investigational device used for diagnosis, when applicable.
 
 
In order to establish the non-relatedness, not all the criteria listed above might be met at the same time, depending on the type of device / procedures and the serious adverse event.

Possible	
The relationship with the use of the investigational device or comparator or the relationship with procedures is weak but cannot be ruled out completely. Alternative causes are also possible (e.g. an underlying or concurrent illness / clinical condition or / and an effect of another device, drug or treatment). Cases where relatedness cannot be assessed or no information has been obtained should also be classified as possible.

Probable	
The relationship with the use of the investigational device or comparator or the relationship with procedures seems relevant and / or the event cannot reasonably be explained by another cause.

Causal Relationship	
The serious adverse event is associated with the investigational device, comparator or with procedures beyond reasonable doubt when:
 
 
the event is a known side effect of the product category the device belongs to or of similar devices and procedures.
 

	Clinical Investigation Plan		
	Investigation No: 5078401	Protocol Version: V2.0 08-Jun-2023	Page 48 of 62

	
 
▪ the event has a temporal relationship with investigational device use / application or procedures.
 
▪ the event involves a body-site or organ that: 
 
○ the investigational device or procedures are applied to
 
○ the investigational device or procedures have an effect on
 
 
 
▪ the serious adverse event follows a known response pattern to the medical device (if the response pattern is previously known).
 
▪ the discontinuation of medical device application (or reduction of the level of activation / exposure) and reintroduction of its use (or increase of the level of activation / exposure), impact on the serious adverse event (when clinically feasible).
 
▪ other possible causes (e.g. an underlying or concurrent illness / clinical condition or / and an effect of another device, drug or treatment) have been adequately ruled out.
 
▪ harm to the subject is due to error in use.
 
▪ the event depends on a false result given by the investigational device used for diagnosis, when applicable.
 
 
In order to establish the relatedness, not all the criteria listed above might be met at the same time, depending on the type of device / procedures and the serious adverse event.

--	---

For each AE a severity description should be given.

Severity	Description
Mild	The event is easily tolerated and does not limit everyday activities; the subject may experience slight discomfort.
Moderate	The event is sufficiently discomforting to interfere with everyday activities.
Severe	The event prevents normal everyday activities; the subject may experience intolerable discomfort or pain.

Expectedness for each AE will be determined based on the information in section 6 of the Investigator's Brochure.

Coding of AEs and medical history will be done using Medical Dictionary for Regulatory Activities (MedDRA) 26.0, or the most recent version if this has changed. If there is an update to MedDRA during the course of the investigation the most recent version will be used by <insert vendor name>. Concomitant medications are coded by the CRO using the WHO dictionary (including ATC coding).

	Clinical Investigation Plan		
	Investigation No: 5078401	Protocol Version: V2.0 08-Jun-2023	Page 49 of 62

